### **1.16 Data Analysis**

Separate data summaries will be prepared for each cohort:

- Demographic and medical history data will be summarized. For quantitative variables, summaries will include the sample size, mean, median, standard deviation, minimum, and maximum. For qualitative variables summaries include the number and percent of patients for each outcome.
- Exploratory analyses will include the observed response and the change from baseline to each of the post-infusion time points for each of the laboratory tests (hematology, coagulation, platelet and chemistry). Additionally, summaries of the number and percent of patients with both a change of  $>5\%$  from baseline and whose results are outside of reference ranges will be displayed. For quantitative variables summaries of the observed response and the change from baseline to each of the post-baseline time points will include the sample size, mean, median, standard deviation, minimum, and maximum. Additionally, for the change from baseline summaries, the statistical significance will be determined using either a t-test or the Wilcoxon Signed Rank test, as appropriate. Summaries for qualitative variables will include the number and percent of patients for each outcome.
- Incidence of AEs and SAEs per patient and by body system will be summarized showing the number and percent of patients for each outcome. Summaries will also be prepared by severity and relationship to treatment.
- Summaries of vital signs and clinical data including WHO bleeding scores will include the observed response and the change from baseline to each of the post-infusion time points for each of the variables. For quantitative variables summaries of the observed response and the change from baseline to each of the post-baseline time points will include the sample size, mean, median, standard deviation, minimum, and maximum. Additionally, for the change from baseline summaries, the statistical significance will be determined using either a t-test or the Wilcoxon Signed Rank test, as appropriate. Summaries for qualitative variables will include the number and percent of patients for each outcome.

A statistical analysis plan will be developed as part of the data analysis plan.

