### 8.3 Clinical Laboratory Assessments

Laboratory assessments to be used in safety monitoring will include coagulation, hematology, and serum chemistry measures. For each assessment type, descriptive statistics summarizing the raw and CFB values of all measures (or select measures, see Hematology below) will be provided in 2 tables. As the Wilcoxon signed rank test will be used to test for difference between baseline and post-baseline values, the P-values derived during testing will be displayed within these tables, adjacent to corresponding CFB values. In 2 additional tables, the numbers and percentages of patients who show abnormal results and who show changes (shifts) from baseline in interpreted results (normal, abnormal non-clinically significant, and abnormal clinically significant) will be summarized per measure and visit. Measures corresponding to each assessment type will include those listed below, given sufficient data available for descriptive analysis (i.e., minimally 3 data points per computed statistic for each of 2 or more visits).

- **Coagulation:** PT, INR, aPTT, D-dimer, fibrinogen, TAT, PF 1+2, TEG (R time, K time, MA, angle), ROTEM (CT, CFT, angle, MCF), and TGA (lag time, time to peak, thrombin peak height, ETP)
- **Hematology:** WBC, RBC, hemoglobin, hematocrit, platelets, MPV, neutrophils, lymphocytes, monocytes, eosinophils, and basophils
  - Descriptive summaries of raw values will be presented in a single table for the select measures of WBC, RBC, hemoglobin, hematocrit, platelets, and MPV.
  - Descriptive summaries of CFB values and Wilcoxon signed rank test results will be presented in a single table for the select measures of WBC, neutrophils, lymphocytes, monocytes, eosinophils, and basophils.
- **Chemistry:** blood glucose, BUN, creatinine, sodium, potassium, chloride, calcium, CO2, alkaline phosphatase, AST (SGOT), ALT (SGPT), total bilirubin, GGT, albumin, LDH, total cholesterol, total protein, and hs Troponin I (or hs Troponin T)

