## 9.1 Clinical Laboratory Assessments

Laboratory assessments to be used in efficacy analyses will include select hematology measures (hemoglobin, hematocrit, and platelets). Within a single table for each of 2 populations (Safety and Evaluable), the numbers and percentages of patients will be presented by categorized patterns of post-infusion change, including clinical improvement, stability/no change, and clinical worsening, for each of 2 post-infusion timeframes (infusion through the 24-hour post-infusion visit and infusion through the Day-6 visit). For each patient, categorization will require consideration of all measurements recorded across all time-points within the timeframe. For each hematology measure, clinical improvement and worsening will be defined as shown below. The category of stability/no change will apply by default when, for an individual patient, neither improved nor worsened conditions have been observed following infusion. When both improved conditions and worsened conditions have been distinctly observed at different time-points, the patient will fall into the category of clinical improvement.

Clinical improvement will be defined by:

- Hemoglobin increase of 1 g/dL
- Hematocrit increase of 3%
- Platelet count increase of 5,000/ $\mu$ L

Clinical worsening will be defined by:

- Hemoglobin decrease of 1 g/dL
- Hematocrit decrease of 3%
- Platelet count decrease of 5,000/ $\mu$ L

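### Five of 11 hematology measures, including platelets, hemoglobin and hematocrit, have no continuous change-from-baseline summary or test, contrary to Protocol 1.16 and without explanation

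*SAP*

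**What the plan says.** SAP 8.3 sets a general rule for laboratory data with an exception for hematology: "descriptive statistics summarizing the raw and CFB values of all measures (or select measures, see Hematology below) will be provided in 2 tables". Coagulation and chemistry fall under the general rule, so all their measures get both kinds of summary, given sufficient data.

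For hematology the SAP lists "WBC, RBC, hemoglobin, hematocrit, platelets, MPV, neutrophils, lymphocytes, monocytes, eosinophils, and basophils". It then splits them:

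- Raw values: "Descriptive summaries of raw values will be presented in a single table for the select measures of WBC, RBC, hemoglobin, hematocrit, platelets, and MPV".
- Change from baseline and signed-rank results: "will be presented in a single table for the select measures of WBC, neutrophils, lymphocytes, monocytes, eosinophils, and basophils".

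The planned output for the second group is Table 14.3.5.2 in SAP Appendix 2. Its title does not show that it covers only some of the measures.

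Protocol 1.16 is wider. Its exploratory analyses include "the change from baseline to each of the post-infusion time points for each of the laboratory tests (hematology, coagulation, platelet and chemistry" groups, and it adds that "for the change from baseline summaries, the statistical significance will be determined using either a t-test or the Wilcoxon Signed Rank test, as appropriate".

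SAP 9.1 uses three of the omitted measures for efficacy: "Laboratory assessments to be used in efficacy analyses will include select hematology measures (hemoglobin, hematocrit, and platelets". These are reported as counts of patients who improve, stay stable or worsen.

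**The concern.** The measures left out of the change table are the ones on which the SAP itself relies elsewhere. Hemoglobin, hematocrit and platelets are its only efficacy laboratory measures, and SAP 2.2.1 makes directional change in hematology part of a primary endpoint. Protocol Table 5 lists thrombocytopenia and platelet antibody formation among the possible risks of blood-product infusion that may also apply to Thrombosomes.

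The product is not expected to raise the platelet count increment (Protocol 1.9.2.2), so the value of a change summary lies mainly in detecting a fall after infusion. If such a fall occurred, the report would give no average size for it, no spread of within-patient change and no test. It would give all of these for basophils.

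**Working it through.** No sample-size or power figure is at issue. The check compares lists of measures and then asks what each remaining output can show.

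**1. Coverage of the 11 measures (SAP 8.3 and 9.1).**

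| Measure | Raw summary | Change summary and test | Shift table | SAP 9.1 category | Individual plot |
|---|---|---|---|---|---|
| WBC | yes | yes | yes | no | yes |
| RBC | yes | no | yes | no | no |
| Hemoglobin | yes | no | yes | yes | yes |
| Hematocrit | yes | no | yes | yes | no |
| Platelets | yes | no | yes | yes | yes |
| MPV | yes | no | yes | no | no |
| Five differential counts | no | yes | yes | no | no |

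The change table holds 1 + 5 = 6 measures, so 11 − 6 = 5 are missing. Only WBC is in both tables: five measures have raw values without change, and five have change without raw values.

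**2. Against the protocol.** Protocol 1.16 covers each laboratory test, so meeting it would mean 11 of 11. SAP Section 11 has entries for objectives, endpoints, enrollment definitions, patient numbers and sample size, and none for this reduction.

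**3. What the remaining outputs can show.**

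- *SAP 9.1 categories.* The thresholds are 1 g/dL for hemoglobin, 3% for hematocrit and 5,000/µL for platelets, with no test. The tie rule is: "When both improved conditions and worsened conditions have been distinctly observed at different time-points, the patient will fall into the category of clinical improvement". Take a patient whose platelets are 5,000/µL below baseline at 1 hour and, after a platelet transfusion, 5,000/µL above baseline at 24 hours. Both thresholds are met and the patient is counted as improved. Protocol 1.9.2.2 restricts platelets only from six hours before to one hour after infusion, and lifts all limits if bleeding is unchanged or worse, so this sequence is possible.
- *Shift table (14.3.5.4).* The categories are normal, abnormal not clinically significant, and abnormal clinically significant. A patient in the last category at baseline cannot shift further down. All patients enter with platelets of 70,000/µL or less. How many would be graded clinically significant at baseline is not stated.
- *Spaghetti plots.* These show individual raw values for hemoglobin and platelets, without a numerical summary of change. Hematocrit, RBC and MPV are not plotted.
- *Raw summaries by visit.* Days 3 to 5 are collected only in hospitalized patients, so the mean at those visits may describe different patients from the baseline mean. Paired change compares each patient with their own baseline.

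**4. Can the planned test work at this size?** With n non-zero, untied differences, the smallest exact two-sided signed-rank p-value is 2/2^n.

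- n = 8: 2/256 = 0.0078, below 0.05.
- n = 6: 2/64 = 0.031, below 0.05.
- n = 5: 2/32 = 0.0625, above 0.05.

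A full cohort can reach 0.05. A row cut to five or fewer patients cannot.

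**5. Added tests.** 5 measures × 4 fixed post-baseline visits (1 h, 6 h, 24 h, Day 6) × 4 groups (three cohorts and all patients) = 80 p-values, or 80 × 2 = 160 if each is run with and without post-transfusion values. SAP 6.7 plans no multiplicity adjustment.

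**The case against.** The restriction is written out as a selection. The protocol calls these analyses exploratory and leaves detail to a SAP, and Section 11 says that it lists only the most significant departures. With eight patients per cohort, individual plots by cohort and by transfusion subgroup, together with full listings, let a reader follow every hemoglobin and platelet trajectory. The SAP endpoint itself accepts graphics as an alternative to statistics. Blood products given after infusion change these measures directly, so a plain one-sample test would mix transfusion and product effects. Marking post-transfusion values would not say how a mean or p-value treats them.

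Much of this stands. A reader might infer that paired change in platelets and hemoglobin is never summarised numerically; that is wrong, because SAP 9.1 tabulates change categories for two timeframes and two populations, and the shift table adds counts by visit. A reader might also treat the entry limits for platelets (70,000/5,000 = 14-fold) as the spread that raw means would face. They are eligibility limits, the documents give no standard deviation, and they say nothing about the other four measures. The earlier study's platelet comparison is limited support, since it compared changes between treated and control healthy volunteers. Nor do the documents make a platelet fall the leading safety signal: the stopping rules name death, thrombotic or embolic events, acute lung injury and anaphylaxis.

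What does not stand is the step from transfusion confounding to omission. Transfusion affects the raw means and the SAP 9.1 categories just as much, and the SAP keeps those. It calls for a stated rule.

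**Conclusion.** The concern holds in this limited form. Five of 11 hematology measures lack the continuous change summary and test that Protocol 1.16 plans, and the SAP neither explains nor logs this. The outputs that remain for hemoglobin, hematocrit and platelets do describe change, but imperfectly and in ways that can miss or mask a fall. For RBC and MPV, only the shift table addresses change.

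The documents do not show whether the omission was an oversight or a choice, and nothing in them supports reading it as concealment: the listings and plots disclose the data. The effect on conclusions cannot be sized, because it depends on how many patients are transfused after infusion and how many are graded clinically significantly abnormal at baseline, and neither figure is given. This is a gap in reporting within an exploratory safety analysis and does not invalidate the design.

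**What to change.** Add RBC, hemoglobin, hematocrit, platelets and MPV to Table 14.3.5.2, with descriptive change from baseline and the planned signed-rank test, labelled exploratory. Show each measure twice:

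- with all values;
- excluding values taken after a post-infusion transfusion of a product that directly affects the measure: platelet products for platelets and MPV; red cells or whole blood for hemoglobin, hematocrit and RBC.

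Show n in every row. Both versions are needed because exclusion is not neutral: patients whose values fall may be those who are transfused. Record the change in SAP Section 11. If the sponsor prefers to keep the restriction, it should at least state the reason there.

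No new data are needed. SAP 6.3 already defines change from baseline. The transfusion subgroups in SAP 6.6 already require transfusion times relative to infusion, and Protocol Table 4 requires blood counts before and after each post-infusion transfusion through Day 6. The costs are more table rows, the unadjusted p-values counted above, and smaller n in the transfusion-excluded rows, some of which may be too small for the test to reach 0.05. The descriptive change should therefore be read first.

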Routine Chemistry: Na, K, Cl, CO2, Glucose, BUN, Creatinine, Albumin, Total Bili, Ca, AST, Alkaline Phosphatase, ALT, GGT, LDH, Total Cholesterol, Total Protein			X		X	X					
Special Chemistry hsTroponin I or T Assay			X		X	X					
Draw archive sample	X									X	

Evaluation	Initial Screen	Rescreen (if applicable  )	Day 1  Base Line -2 hr pre-infusion	1 hr post infusion ± 15min	6 hr post -1 or +2 hr	Day 2 24 hr post ± 3 hr	If hospitalized			Day 6 (+ 4 days)	Day 30 (+2 days) (by phone)								
							Day 3	Day 4	Day 5										
 Rescreening performed on those patients who passed eligibility criteria, were not actively bleeding at time of initial screen, and started bleeding within 4 weeks. Patients who were initially screened within 4 days (+6 hrs) do not need to be re-screened except for WHO bleeding assessment and CBC.																			
 Baseline may occur on the same day (within 24 hours) as either Initial Screen or Rescreen. The WHO assessment, CBC and coagulation must be collected at baseline, not more than 2 hours prior to infusion. Red cell transfusion must be specifically related to treatment of bleeding within 24 hours of onset of bleeding.																			
 Chart review for SAEs (only) needs to include data from day 1 though Day 30 (+2 days). Phone call with patient is to confirm if the patient had an SAE or required emergency medical care at an outside facility.																			
 Complete physical exam to include height, weight, general assessment of health by history and medical exam including neurological exam. History to include previous transfusion with red blood cells, plasma and/or platelets.																			
 Abbreviated Physical Exam to include general appearance, cardiovascular, respiratory, extremities, abdomen and head and neck.																			
 In the event of the transfusion of a blood component after infusion of Thrombosomes on Days 1-6, CBC results are required from a sample collected within 8 hours or less prior to the transfusion and within 1-hour (+30 min) post transfusion.																			
 Daily CBC required, but ALL CBC data for each patient during the hospitalization phase through Day 6 must be collected and entered into the database.																			
 If TEG or ROTEM testing is available, include samples for the record.																			

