### ***1.15.3 Drawing Blood Samples from Patients***

The samples to be collected from the patient for this study are listed below. Blood will be collected according to policies at each site or central laboratory, in tubes and volumes per site specifications, and will be listed in the informed consent form for that site. For each of the timepoints that require archive samples, two 10 ml samples will be drawn; one for plasma (EDTA) and one for serum.

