## Appendix C- Definition of Myocardial Infarction

Definition of Myocardial Infarction (two or more of the following):

1. hs Troponin I or hs Troponin T level greater than the local lab reference range for normal.
2. Electrocardiograms (EKGs; at least two) showing changes from baseline or serially in ST-T and/or Q-waves that were 0.03 seconds in width and/or greater than one-third of the total QRS complex in two or more contiguous leads.

**NOTE:** Other EKG findings consistent with a diagnosis of myocardial infarction may also be considered a myocardial infarction.

[figure not shown]
3. Clinical indications consistent with myocardial infarction as seen by prolonged (> 20 min) chest pain not relieved by rest and/or nitrates
4. Radiologic evidence as seen by
  - A. Angiographically documented coronary artery occlusion, or
  - B. Imaging evidence of loss of viable myocardium

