-  Blood products may include packed red blood cells, whole blood, apheresis platelets, pooled whole blood derived platelets, cryoprecipitate, and plasma. In the event of a blood product transfusion occurring after Thrombosomes infusion on Days 1-6, CBC results will be required from a blood sample collected within 8 hours prior to transfusion and within 1 hour (+30 min) following transfusion.
-  Hematology CBC analytes will include WBC, RBC, hemoglobin, hematocrit, platelets, MPV, neutrophils, lymphocytes, monocytes, eosinophils, and basophils. Daily CBC will be required, but all CBC data for each patient during hospitalization through Day 6 will be collected.
-  During screening, coagulation testing will include only PT/INR, aPTT, D-dimer, and fibrinogen. At and following baseline, testing will include PT/INR, aPTT, D-dimer, fibrinogen, TAT, PF 1+2, TEG or ROTEM, and TGA. For baseline testing, PT/INR, aPTT, D-dimer and fibrinogen will be collected no more than 8 hours prior to infusion.
-  EKG measures include only heart rate and QT interval with Fridericia's correction. The EKG will be repeated if performed more than 4 days before infusion.
-  For each of the time-points that require archive samples, 2 10-mL samples will be drawn (1 for plasma and 1 for serum).
-  Medications may include but will not be limited to over-the-counter remedies, herbal preparations, vitamins, supplements and intravenous fluids.
-  Vital signs will include heart rate, respiratory rate, systolic and diastolic blood pressure, and body temperature.
-  Routine chemistry will include Na, K, Cl, CO2, glucose, BUN, creatinine, albumin, total bilirubin, Ca, AST, alkaline phosphatase, ALT, GGT, LDH, total cholesterol, and total protein. Special chemistry will include hs Troponin I and hs Troponin T.

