Results for select coagulation and hematology measures will also be provided in panels of spaghetti plots, with each panel corresponding to a single measure and incorporating 3 plots per row (1 plot for each patient cohort) and each plot presenting an overlay of the raw assessment results for individual patients through time. For each measure, 2 separate panels in total will be constructed. In the first panel (1 row x 3 columns and up to 1 page in length), individual patients will be represented without subgrouping. In the second panel (3 rows x 3 columns and up to 3 pages in length, given 1 row per page), line colors or patterns will be used to distinguish patients as belonging to Subgroup 1 or 2 (did or did not receive anticoagulant therapy; row 1), Subgroup 3 or 4 (did or did not receive platelet transfusion; row 2), and Subgroup 5 or 6 (did or did not receive any blood product transfusion other than platelets; row 3). Panels will be constructed for all measures listed below, given available data.

- Coagulation: INR, aPTT, D-dimer, fibrinogen, TAT, PF 1+2, TEG R time, TEG MA, TGA time to peak, and TGA thrombin peak height
- Hematology: WBC, hemoglobin, and platelets

Pertaining solely to the measure of WBC count, a single table will be produced to provide descriptive summary of the numbers and percentages of patients with abnormal results by visit and living status (Subgroup 7 vs. 8; see Section 6.6). Given the potential for lab normal ranges (and, thus, classification of WBC count results as abnormal) to differ across study sites, a second table will display the numbers and percentages of patients at different WBC count levels (defined using quantiles of raw WBC counts across all measurements, patients, and sites) by visit and living status. To facilitate visual examination of trend, this latter summary may also be presented within a supplementary clustered bar chart, line chart overlay, or panel of survival curves. Lastly, multiple data listings will be produced to disclose the details of sample collection and results for all clinical laboratory assessments performed per patient.

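### SAP 8.3 treats high-sensitivity troponin I and troponin T as one chemistry measure, so raw means and changes by cohort could combine two analytes; they need separate rows.

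*SAP*

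**What the plan says.** SAP 8.3 plans, for each laboratory type, "descriptive statistics summarizing the raw and CFB values of all measures". It adds that "the Wilcoxon signed rank test will be used to test for difference between baseline and post-baseline values", with the P-values printed beside the changes. In the chemistry list troponin is one entry: "hs Troponin I (or hs Troponin T".

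Other places bear on how that entry would be filled:

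- Protocol Table 4 asks for a "hsTroponin I or T Assay" at baseline, 6 hours and 24 hours, so either assay satisfies the schedule.
- The footnote on chemistry under SAP Table 2 reads differently: "Special chemistry will include hs Troponin I and hs Troponin T".
- Protocol Appendix C makes one criterion for myocardial infarction "hs Troponin I or hs Troponin T level greater than the local lab reference range for normal", so the yardstick is local.
- SAP 6.3 defines change from baseline as a plain subtraction in the units reported. SAP 8 gives results per cohort and for all patients together. SAP 6.5 plans no stratified or adjusted analysis.
- SAP 2.2.1 counts the central tendency and variability of serum chemistry measures, by dose level and overall, among the primary endpoints.

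**The concern.** Troponin I and troponin T are two analytes, each with its own assay and reference limit. The study is multicenter and a site may run either one. If both feed one row, the cohort mean is an average over two scales, and the mean change is dominated by patients on the assay with the larger numbers. Cohorts fill in order of enrollment, so the share of patients on each assay may differ from one dose level to the next. A difference between dose levels in the troponin table could then come from the assay mix, or a real one could be masked.

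Troponin is the laboratory marker in the protocol's definition of myocardial infarction, and the protocol asks investigators to watch for vascular occlusion, including heart attack. The affected table also supports a listed primary endpoint.

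The SAP already handles a similar case by separation: TEG and ROTEM, which the schedule accepts as alternatives, are listed in 8.3 with their own parameters. Troponin I and T are not.

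**Working it through.** The plan states no figure to reproduce on this point; its sample size was not statistically derived. The checks below show the mechanism. Every scale factor (r or k) and every site mix is an assumption.

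**1. Raw cohort means.** Eight patients per cohort (SAP 3.1), identical biology, second assay reading r times the first. With 2 of 8 patients on the second assay the relative mean is (6 + 2r)/8; with 6 of 8 it is (2 + 6r)/8.

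| r | 2 of 8 | 6 of 8 | spurious difference |
|---|---|---|---|
| 1.2 | 1.05 | 1.15 | 9.5% |
| 1.5 | 1.125 | 1.375 | 22% |
| 2 | 1.25 | 1.75 | 40% |

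The 6:2 mix, if it arises from two sites, is a ratio of 3:1, inside the 1:5 limit in SAP 4.

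**2. Mean change.** Baseline 10 for all; relative changes +30, +25, +20, +15, −10, −12, +8 and +5%. On one scale the mean change is 10 × 0.81/8 = 1.01. The first four relative changes sum to 0.90 and the last four to −0.09.

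- First four on the second assay: 10 × (0.90k − 0.09)/8 = 2.14, 5.51 and 11.14 for k = 2, 5 and 10.
- Last four on the second assay: 10 × (0.90 − 0.09k)/8 = 0.90, 0.56 and 0.00.

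**3. Signed-rank P-value, same eight patients, exact two-sided.** On one scale the two negative changes hold ranks 3 and 4, a rank sum of 7, and P = 38/256 = 0.148. With the first four on the second assay the ranking does not change and P stays 0.148 at every k. With the last four, P becomes 0.328, 0.727 and 0.742 for k = 2, 5 and 10.

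Scaling changes the ranks of the absolute changes, never their signs. If all eight changes share a sign, P = 2/2^8 = 0.0078 at any k. A purely additive offset between assays cancels in the changes.

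**4. Error rates.** In 6,000 simulated cohorts of eight per setting, with normally distributed changes and four patients multiplied by k:

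- No true change: rejection at 0.05 is about 3% to 4%, mixed or not.
- True shift of 0.8 SD:

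| k | one scale | mixed | 0.05 decision differs |
|---|---|---|---|
| 2 | 42.7% | 41.8% | 7.5% |
| 5 | 42.2% | 37.0% | 15.4% |
| 10 | 43.3% | 35.6% | 18.3% |

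**5. Cost of separating.** The smallest two-sided P for n patients is 2/2^n: 0.125 at n = 4, 0.0625 at n = 5 and 0.031 at n = 6. In an even 4:4 split neither row can reach 0.05.

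**The case against.** The strongest reply is that the safety signal does not rest on pooled means. SAP 8.3 also tabulates abnormal results and shifts in the interpreted result, and SAP 2.2.1 makes a shift to a clinically significant abnormality a primary endpoint. Thromboembolic events are captured as adverse events, with their own listing and a stopping rule. The committee that reviews each dose step receives listings of selected chemistry results. This stands, and it limits the harm to the descriptive troponin tables.

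It is also fair that the SAP never says I and T share a row; the bracketed wording may mean only whichever assay was reported. That makes the problem one of a missing rule, which a programmer would have to supply.

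Four stronger readings are tempting, and the documents do not support them.

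- *The P-values are invalid.* They are not: the test is within patient and its type I error holds. The effect is on weighting and power, and it is small at k = 2.
- *A formal dose comparison is distorted.* SAP 8.3 plans no between-cohort test of laboratory values. A different site mix by dose is possible, not certain.
- *The SAP concedes that raw scales differ between sites.* The sentence beginning "Given the potential for lab normal ranges (and, thus, classification of WBC count results as abnormal) to differ across study sites" concerns abnormal flags for white cell count, and its remedy is to pool raw counts across sites. It is no admission about raw scales.
- *D-dimer and the other coagulation tests have the same fault.* Protocol 1.15.3 says "Blood will be collected according to policies at each site or central laboratory", and the section on testing departments (Protocol 1.2) is not in the text available here. Those tests may be central. Where assays agree and only ranges differ, dividing by each site's limit would add noise.

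**Conclusion.** The point holds for troponin. Taken literally, SAP 8.3 lets raw means and native-unit changes combine two analytes, and the protocol schedule and the SAP Table 2 footnote disagree on whether one assay or both will be run. If all sites ran the same assay on the same scale, nothing would be distorted.

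If they did not, the size depends on a scale factor that the documents do not give. Cohort means could differ by 9.5% to 40% for assumed factors of 1.2 to 2 under opposite 6:2 mixes. Mean changes could move either way, and power at a 0.8 SD shift could fall by about 1 to 8 percentage points for factors of 2 to 10.

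The importance is modest: this is a descriptive Phase 1 study, and the interpreted-result tables and listings carry most of the signal. The correction is worth making because it costs very little and the tables support a primary endpoint.

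**What to change.** - Reconcile *or* (Protocol Table 4, SAP 8.3) with *and* (the SAP Table 2 footnote), and state which assay or assays are collected and in what units.
- In SAP 8.3, list troponin I and troponin T as two measures, with separate rows for raw summaries, changes and signed-rank tests.
- If a row falls below the SAP's minimum of three data points, add a combined summary of each value divided by the local upper reference limit. This puts the two on a common yardstick but does not make them the same analyte. Keep raw values in the listings.
- State which tests are local and which are central. Only if D-dimer or other coagulation tests are run locally on assays or units that cannot be compared, add the same scaled summary for them as a supplement to the raw tables.

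The cost is a few sentences of SAP text and some programming, with no new data collection beyond local reference limits, which the protocol's own out-of-range counts (1.16) already need. The downsides are smaller numbers per troponin row, with P-values that may be unable to reach 0.05, and a scaled unit that clinicians know less well.
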